12.6 Safety Analyses

12.6.1 Adverse Events

All AEs will be coded using MedDRA Version 24.0 or later. A TEAE is defined in Section 10.6. Only TEAEs will be included in AE summaries unless otherwise specified. All adverse events (including non-treatment-emergent events) recorded on the CRF will be listed. All AE summary tables will be provided for each treatment and total group in the SS.

All AE summaries will include the number and percentage of subjects in each category. For the calculation of the incidence of events, subjects will only be counted once within the events. For summaries and PT, subjects will be counted once per unique PT and SOC. The number of events in each category will also be presented. For summaries by SOC and PT tables should be sorted in descending order of SOC and then PT by subject counts in the total group.

An overall summary of treatment-emergent adverse events will be presented for the following categories:

- Any TEAEs
- Any Serious Adverse events (SAE)
- Severe TEAEs
- Related TEAEs
- TEAEs pattern (continuous, intermittent, single event)
- TEAEs leading to discontinuation of IMP
- TEAEs leading to trial withdrawal
- TEAE with outcome of death (events with outcome of Fatal on the AE CRF page)

The risk difference between treatments will be calculated for the above categories (except for TEAEs patterns) for the comparison of treatment groups and will be presented together with the 95% Wald asymptotic CI for this risk difference. Risk difference will also be presented for selected SOC and PT if deemed of interest prior to lock.

In addition, the following summaries by SOC and PT will be produced:

- TEAEs
- SAE
- Related TEAEs
- Related SAEs
- Severe TEAEs
- TEAEs leading to discontinuation of IMP
- TEAEs leading to trial withdrawal
- AEs leading to death
- Related AEs leading to death
- TEAEs occurring in 5% of subjects (based on PT) in any treatment arm
- Non-Serious TEAEs occurring in 5% of subjects (based on PT) in any treatment arm

A tabulation of TEAEs, categorized by relationship to IMP, will also be presented. Subjects with multiple events within a particular SOC or PT will be counted under the category of their most drug-related event within that SOC or PT. Then the relationship to IMP is dichotomized into related or not related as defined in Section 10.6.

A summary of events reported, categorized by severity (mild, moderate or severe as recorded on the AE CRF page), will also be provided. Subjects with multiple events within a particular body system or PT will be counted under the category of their most severe event within that body system or PT.

A further tabulation presenting the preferred terms for the events in descending order of frequency for the treatment group will also be presented.

Listing of AEs leading to death, IMP discontinuation, trial discontinuation and SAEs will be provided. If a subject has missing severity or seriousness in the database they will be treated as worst-case i.e. severe and serious respectively.

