CRP was initially selected as the primary endpoint because CRP has been reported to predict severe disease ([Tan et al., 2020](#); [Wang, 2020](#)) and mortality ([Ruan et al., 2020](#)) in COVID-19. However, there was a rapid and profound decrease in CRP in both the C21 and the placebo group, most likely because the patients were treated with glucocorticoids which became part of standard of care at the time of trial initiation likely leading to no statistical difference in the primary endpoint CRP. Nevertheless, in the patients with more pronounced respiratory distress with need of supplementary oxygen at baseline, there was a small but significantly greater reduction of CRP in the C21 than in the placebo group.

There were 64 treatment-emergent AEs reported by 60.8% of the patients in the C21 group and 90 events reported by 67.3% of the patients in the placebo group. Most events were mild, and no event in either group was classified as related to trial treatment by the investigators. The most frequent AE was hyperglycemia, which occurred more frequently in the C21 group than in the placebo group. The level of hyperglycemia was predominantly mild and not reported as related to C21 by investigators.

Taken together, C21 on top of standard of care, including glucocorticoids and remdesivir, significantly improved respiratory function reflected by a reduced need for supplemental oxygen in hospitalized COVID-19 patients.

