8.0 Trial Design

This is a randomized, double-blind, placebo-controlled, parallel-group, 2-arm, multicenter trial to evaluate the efficacy and safety of C21 versus placebo as add-on to the SoC in adult subjects with COVID-19.

The trial will enroll a maximum of 300 randomized subjects, up to 150 per arm (oral C21 100 mg twice a day (b.i.d.) or placebo for 14 days) according to a 1:1 randomization. Randomization occurs at visit 2 (Day 1) and will be stratified by:

- Disease severity (based on the 8-point ordinal scale score at Day 1 with a score of 5 or 6).
- Region (North America, South and Central America, Europe, Asia, Africa).

Approximately 350 subjects will be screened to achieve a maximum of 300 enrolled and randomly assigned subjects to investigational medicinal product (IMP) treatment.

Subjects hospitalized due to ongoing COVID-19 and who have a score of 5 or 6 on the 8-point ordinal scale will be enrolled. The trial consists of 3 consecutive periods (Table 1): a screening period of up to 48 hours, a 2-week IMP treatment period and a follow-up period of up to 7 weeks. Daily visits are required until discharge. Discharged subjects should return to the clinic for the Day 15 visit. Days 8, 22, 29 and 60 visits will be conducted as phone or video visits for all discharged subjects. The trial duration for an individual subject will not exceed 9 weeks. End of trial is defined as the last subject's last follow-up visit.

An independent data monitoring committee (DMC) will actively monitor data from the trial and will review unblinded safety data from the trial after data collection for 15 days on the first 150 randomized subjects. In addition, the DMC members may call for an ad hoc safety review meeting at any time during the trial.

All subjects will undergo a series of efficacy, safety, and laboratory assessments. Laboratory samples will not be collected at Days 3, 5, 8 and 11 if the subject is discharged from hospital prior to the visit. The primary endpoint is all-cause mortality up to Day 60. The key secondary endpoints are time to sustained hospital discharge up to Day 60, supplemental oxygen free days up to Day 29, the proportion of subjects free of respiratory failure at Day 15 and proportion of subjects discharged from hospital and free of supplemental oxygen at Day 15. Type 1 errors will be controlled using a fixed sequential testing hierarchy.

Table 1: Schedule of Activities (SoA)

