9.5.4 Safety Analysis Set

The safety analysis set (SS) is defined as all subjects who are exposed to at least one dose (even partially) of the IMP. Subjects will be analyzed according to the intervention received.

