12.0 Statistical Methods

All statistical analyses will use SAS® version 9.4 or higher. Unless otherwise noted, categorical variables will be summarized using counts and percentages. Percentages will be rounded to one decimal place, except 100% which will be displayed without any decimal places and percentages will not be displayed for zero counts.

Continuous variables will be summarized using the number of observations (n), mean, Standard Deviation (SD), median, Q1, Q3, minimum and maximum. The minimum and maximum values will be displayed to the same level of precision as the raw data, the mean, median, Q1, and Q3 to a further decimal place and the SD to two additional decimal places. The maximum number of decimal places will be 4, unless otherwise noted. P-values will be presented to 3 decimal places, with values less than 0.001 presented as <0.001.

In general, all data summaries will be presented by treatment group and overall. Efficacy outputs will not have an overall column. If not stated otherwise, p-values from statistical tests will be two-sided and CIs will be calculated using a 95% CI.

Stratification will be done based on baseline disease severity, that is the score on the ordinal scale at baseline (5 or 6), and region (North America, South and Central America, Europe, Asia, Africa). The actual stratification will be used as factors in the statistical analysis, subjects included in wrong stratum at randomization will be moved to their correct strata belonging in the analyses. Small stratum may be pooled in the analysis. Any pooling of stratum will be agreed prior to unblinding of the database. Region will be pooled as Europe vs the rest of the world (North America, South and Central America, Asia, Africa). For all models where region is a factor (including in the imputation), pooled region will be used. In the text of this document, region will mean pooled region. Factors may be removed from models if the factor is causing an issue with convergence. For subgroup analysis, factors that are aligned with the strata division will be deleted from the model.

Missing data will be handled as described in Section 10.19. The ITT is used to analyze endpoints related to the efficacy objectives, the PP will be used for sensitivity analyses related to efficacy objectives and the SS is used to analyze the endpoints and assessments related to safety. PK analyses will be presented using the PKS.

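### The Wald intervals planned for adverse-event risk differences have zero width when neither arm has an event, and are too narrow when one arm is close to zero

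*SAP*

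**What the plan says.** SAP 12.6.1 lists eight rows for the overall TEAE summary. For all but the event-pattern row, so for seven rows, it plans a between-arm risk difference with a "95% Wald asymptotic CI for this risk difference". Those seven include related TEAEs and TEAEs with a fatal outcome. A further sentence adds: "Risk difference will also be presented for selected SOC and PT if deemed of interest prior to lock". It does not repeat an interval method for these.

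The denominator is the safety set, "all subjects who are exposed to at least one dose (even partially) of the IMP" (SAP 9.5.4). Its size is bounded by SAP 8.0: "The trial will enroll a maximum of 300 randomized subjects, up to 150 per arm".

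Neither document gives a rule for zero or sparse counts in these intervals, or names another method for them. SAP 12.0 suppresses the percentage when a count is zero but says nothing about the confidence interval.

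On expected frequencies, Protocol 2.2 reports phase 2: "There were 64 treatment-emergent AEs reported by 60.8% of the patients in the C21 group", with 67.3% on placebo, and "no event in either group was classified as related to trial treatment by the investigators".

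**The concern.** The Wald interval estimates its variance from the observed proportions. An arm with no events contributes a variance of zero, however few subjects it has. If both arms are empty, the interval shrinks to a point. If one arm is empty, the interval reflects the uncertainty in the other arm only.

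This happens in the rows where the upper limit is the useful result. For a drug-specific harm, one would expect a few events on C21 and none on placebo, and there the Wald upper limit is too low. For related TEAEs, a repeat of phase 2 would put an interval of zero width in the main safety table. Taken literally, it says that any difference has been ruled out.

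**Working it through.** **Inputs.** n = 150 per arm is the maximum in SAP 8.0; the safety set may be smaller. The level is 95%, two-sided, z = 1.96 (SAP 12.0). The documents give no true rates for rare event types, so I assume rates from 0% to 5% per arm. The phase 2 frequencies are in Protocol 2.2 and the mortality planning rates (10% vs 2.5%) in SAP 8.1. The documents state no coverage figure for these intervals, so there is none to reproduce.

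**Formula.** With x1 and x2 events, p1 = x1/n and p2 = x2/n, the Wald interval is p1 - p2 ± 1.96 × √[p1(1 - p1)/n + p2(1 - p2)/n].

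**Zero events in both arms.** Wald: 0 ± 1.96 × 0, so 0 to 0. For the Miettinen-Nurminen limit, the constrained estimates at difference D are D and 0. The limit solves D/(1 - D) = 1.96² × (300/299)/150 = 0.0257, so D = 0.0257/1.0257 = 2.5%. By symmetry the interval is -2.5% to +2.5%. The chance of 0 vs 0 is (1 - p)^300 for a common true rate p: 55% at p = 0.2%, 22% at 0.5% and 5% at 1%.

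**Small counts at n = 150 per arm.**

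| Events | Wald | Miettinen-Nurminen |
|---|---|---|
| 0 vs 0 | 0.0% to 0.0% | -2.5% to 2.5% |
| 1 vs 0 | -0.6% to 2.0% | -1.9% to 3.7% |
| 3 vs 0 | -0.2% to 4.2% | -0.5% to 5.7% |
| 15 vs 4 | 1.9% to 12.8% | 2.0% to 13.5% |

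For 3 vs 0: p1 = 0.02, SE = √(0.02 × 0.98/150) = 0.0114, and the upper limit is 0.02 + 1.96 × 0.0114 = 4.2%.

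**Coverage.** I enumerated every pair of counts from two Binomial(150, p) variables and added the probability of those pairs whose interval contains the true difference.

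| Assumed true rates | Wald | Miettinen-Nurminen |
|---|---|---|
| 0.5% vs 0% | 52.8% | 99.9% |
| 1% vs 0% | 77.8% | 99.6% |
| 1% vs 0.2% | 77.5% | 99.6% |
| 2% vs 0% | 80.1% | 96.8% |
| 3% vs 0% | 93.6% | 95.2% |
| 5% vs 0% | 93.7% | 94.3% |
| 3% vs 1% | 92.3% | 93.8% |
| 1% vs 1% | 97.1% | 97.1% |
| 10% vs 2.5% (planning deaths) | 94.6% | 95.0% |
| 60.8% vs 67.3% (any TEAE, phase 2) | 94.8% | 95.0% |

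Two rows can be checked by hand.

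- At 1% vs 0%, the Wald interval misses whenever no event is seen: 0.99^150 = 22.1%, leaving about 78%.
- At 2% vs 0%, it misses at zero events (0.98^150 = 4.8%). It also misses at one event (150 × 0.02 × 0.98^149 = 14.8%), because the upper limit for 1 vs 0 is 1.97%, just under 2%. That leaves about 80%.

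With one arm at 0%, Wald coverage does not rise steadily with the other rate: it is 93.6% at 3%, 86.5% at 3.25% and 93.7% at 5%. With both arms between 1% and 5% (grid step 0.25%), it ranges from 91.3% to 97.1%, with a mean of 94.6%.

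**The case against.** The strongest reply is that little depends on these intervals. SAP 12.6.1 attaches no test to them, counts and percentages are printed with them, and serious and fatal events are also listed by subject. A reader who sees no events in either arm would hardly take 0 to 0 as proof of no difference. That stands as a limit on the consequence. It does not make the printed interval correct.

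A reader might also infer more than the documents support:

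- **That coverage is about 80% for rare events in general.** It is not. Coverage near or below 80% needs one arm at or near zero and the other at about 2% or less. With equal rare rates (0.5% to 5% in both arms) Wald covers 95.1% to 99.3%. The low figures also rest on assumed rates.
- **That the interval collapses at any zero count.** Zero width needs both arms empty. At 1 vs 0 the interval is too narrow but not degenerate.
- **That fatal TEAEs are a sparse row.** The planning rates imply about 15 vs 4 deaths (0.10 × 150 = 15; 0.025 × 150 = 3.75), and the chance of no death on C21 is 0.975^150, about 2%. Wald performs well there.
- **That related serious events or single preferred terms are assigned a Wald interval.** Related serious events are not among the seven rows. SAP 12.6.2 refers back to 12.6.1 for them without clearly adding a risk difference. For selected SOC and PT a risk difference is promised, but the interval method is left open.

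The related row may also not be empty in this trial. SAP 10.6 counts an event as related when the relationship is missing, and treatment lasts longer than in phase 2. So 0 vs 0 is plausible but not certain.

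**Conclusion.** The point holds in a limited form. The specified method gives a wrong interval at 0 vs 0, and phase 2 makes that outcome plausible for the related-TEAE row. When one arm is near zero and the other is at roughly 0.5-2%, the method can cover far below 95%: about 53% to 80% at the tabulated rates of 0.5%, 1% and 2% vs 0%. With both arms at 1-5% the shortfall is at most about 4 points. For common rows and for deaths at the planning rates there is no material problem.

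The result assumes 150 per arm and true rates that the documents do not supply. A smaller safety set would not remove the zero-width interval: at 100 per arm the score interval for 0 vs 0 is about ±3.7%, since 1.96² × (200/199)/100 = 0.0386 and 0.0386/1.0386 = 3.7%. Nothing here bears on the primary or key secondary analyses. This is a worthwhile correction to the safety tables, not a threat to the trial's conclusions.

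**What to change.** In SAP 12.6.1, replace the Wald interval with the Miettinen-Nurminen score interval for every adverse-event risk difference. State in the same line that it also applies to any risk difference presented for a selected SOC or PT. Using one method throughout avoids a switching rule based on observed counts, and it changes the well-populated rows very little: at 15 vs 4 the limits move from 1.9-12.8% to 2.0-13.5%.

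The cost is one software option and one line of SAP text. Sparse rows will show somewhat wider intervals, such as an upper limit of 5.7% instead of 4.2% at 3 vs 0.

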12.6.2 Deaths and Serious Adverse Events

Death, SAEs, and IMP-related SAEs will be summarized as in Section 12.6.1. Tabulations will be provided by SOC and PT and listings will be prepared for SAEs and AEs leading to death.

12.6.3 Laboratory Data

Laboratory test results will be reported in International System of Units (SI) units. Additionally, summaries will be present for parameters in US units. Only central lab data will be included in the table summaries.

Laboratory values and change from baseline will be summarized using descriptive statistics by time point and treatment group. Laboratory assessments will be grouped for summary as shown in Table 5.

Standard ranges from the central laboratory will be used for the laboratory analysis. The assessment as to if a lab test is low, high, normal as applicable will be derived using the standard ranges for central lab data.

Shift tables of the post-baseline value to high, low, normal will be presented by treatment group, reference range and time point. For categorical urinalysis parameters shift tables will present shifts to normal and abnormal values. Additionally, plots showing the shift from baseline to the maximum/minimum post-baseline value will be presented.

Positive pregnancy results and dip-stick urinalysis results will be provided in a listing.

Table 5. Protocol-required Safety Laboratory Tests

Laboratory Tests	Parameters	
Hematology	Platelet count (thrombocytic particle concentration) Hemoglobin Hematocrit (erythrocyte volume fraction) Mean corpuscular volume (MCV)	White blood cell (WBC) count with differential: Neutrophils Lymphocytes Monocytes Eosinophils Basophils
Clinical chemistry	Blood urea nitrogen (BUN) Glucose, fasting Potassium Sodium	Aspartate transaminase (AST) Alanine transferase (ALT) Alkaline phosphatase (ALP) Albumin

Laboratory Tests	Parameters	
	Calcium Ferritin Prothrombin time (PT) International Normalized Ratio (INR) activated partial thromboplastin time (aPTT)	Total and direct bilirubin Serum creatinine eGFR CRP LDH
Routine urinalysis	
 pH, glucose, protein, ketones, bilirubin, urobilinogen, and specific gravity by dipstick Microscopic examination (per investigator judgment) 	
Pregnancy testing	
 Highly sensitive urine or serum human chorionic gonadotropin pregnancy test (as needed for women of childbearing potential) 	

12.6.4 Vital Signs

Observed values and change from baseline in vital signs will be summarized by time point and treatment group in the SS using descriptive statistics. Parameters to be summarized are body temperature, systolic and diastolic blood pressure, pulse, and respiratory rate. Systolic and diastolic blood pressure will have three readings per visit, the average of the three readings will be used as the analysis value for the visit (note if any of the three readings are missing, the average of non-missing readings will be used).

Body temperature can be measured in degree Celsius or Fahrenheit. In order to summarize body temperature by descriptive statistics, body temperature collected in Fahrenheit will be converted to Celsius prior to the analysis.

Vital signs will be listed in the SS.

12.6.5 Physical Examinations, ECGs, and Other Observations Related to Safety

The physical examination system will be summarized as "normal", "abnormal" with sub category for abnormal events that are clinically significant and the number and percentages of subjects in each category by body system will be presented by time point and treatment group in SS. The assessment of the exam is as reported in the Physical Examination (Body System) CRF page. All physical examination data will be listed.

ECG will only be performed at screening and unscheduled visits. ECG will be summarized for screening, unscheduled visits and "any post-baseline assessment" by treatment group in the SS.

12.7 Pharmacokinetics Analyses

All C21 plasma concentration data collected in this trial may be included in population PK and population PK/PD analyses with the objective of exploring the impact of covariates (e.g., body weight and age) on the PK of C21, or the relationship between the C21 exposure and selected efficacy and safety endpoints. If the PK population is not sufficient for analysis data will be listed only.

Blood PK samples will be collected before the first IMP administration (pre-dose) and 30 minutes, 1, 2, 3, 4, and 6 hours after the first IMP administration. Any population PK and population PK/PD analyses will be reported separately. Due to the unblinding nature of the data, PK analyses will be conducted after unblinding of the trial.

12.7.1 Pharmacokinetic Concentrations

Plasma C21 concentrations below the quantifiable limit (BQL) will be set to $\frac{1}{2}$ the lower limit of quantification (LLOQ) in the computation of mean concentration values. Descriptive statistics (number of subjects,

arithmetic mean, geometric mean, standard deviation, coefficient of variation of the geometric mean, median, minimum, and maximum) will summarize the plasma concentrations by C21 at pre-dose, 30 minutes, 1, 2, 3, 4 and 6 hours post treatment. If 50% of the subjects at a given time point have values BQL then the descriptive statistics will not be presented and will instead display as BQL for the mean and minimum, with the exception of maximum all other statistics will be missing. A figure displaying the mean plasma concentrations over time will be produced.

12.7.2 Pharmacokinetic Parameters

The plasma C21 concentration data will be analyzed by non-compartmental methods with WinNonlin® (WNL) version 8.1 or higher unless stated otherwise and the following parameters will be derived and summarized:

- C_{max} – Observed maximum plasma concentration of C21, expressed in concentration units.
- t_{max} – Time to reach C_{max} following first dose of IMP, expressed in time units. If C_{max} occurs at more than one time point t_{max} will be assigned to the first occurrence of C_{max} .
- $AUC_{(0-6)}$ – Area under the plasma concentration curve from time zero to 6 hours. The below conditions will be followed:
 - Actual time will be used for calculating $AUC_{(0-6)}$
 - If the 6 hour sample was not taken then $AUC_{(0-6)}$ will not be calculated
 - $AUC_{(0-6)}$ will be calculated by WNL using extrapolation to actual time when there is a valid λ_z and the 24 hour sample is BQL and the concentrations thereafter are also BQL.
- $AUC_{(0-\infty)}$ – Area under the plasma concentration-time curve from time zero extrapolated to infinity. Adjusted r^2 for $t_{1/2}$ greater than 0.8 and $AUC\%Extrap \leq 20\%$ are required to obtain a reliable estimation of $AUC_{(0-\infty)}$. $AUC_{(0-\infty)}$ will be included in analysis/summaries only if these two criteria are met.
- AUC_{last} – Area under the plasma concentration curve from time zero to the last quantifiable concentration.
- $t_{1/2}$ – Apparent terminal half-life, expressed in time units. Adjusted r^2 greater than 0.8 is required to obtain a reliable $t_{1/2}$. $t_{1/2}$ will be included in analysis/summaries only if this regression criteria is met (all values will be listed).
- C_6 – Actual plasma concentration of C21 at 6 hours after IMP administration (C_6 will be analyzed using SAS® version 9.4 or higher)

The plasma PK parameters will be estimated from the concentration-time profiles. In estimating the PK parameters, BQL values at the beginning of the profile will be set to zero. BQL values that occur after the first quantifiable point will be considered missing. Values that are embedded between BQLs, or quantifiable values occurring after two or more BQLs, will be set to missing at the discretion of the pharmacokineticist. If an entire concentration-time profile is BQL then the profile will be excluded from PK analysis. Actual sampling times, rather than scheduled sampling times, will be used in all computations involving sampling times. If the actual time or dose time is missing, the scheduled time may be substituted in order to calculate the PK parameter. Descriptive statistics (number of subjects, mean, geometric mean, standard deviation, coefficient of variation, median, minimum, and maximum) will be used to summarize the calculated PK parameters by treatment. For t_{max} , only median, min and max will be presented.

AUCs will be calculated using linear up/ log down (or the linear-log trapezoidal method). The linear trapezoidal method will be employed while concentrations are increasing up to t_{max} . The logarithmic trapezoidal method will be employed after t_{max} while concentrations are decreasing. The minimum requirement for calculation of AUCs will be three consecutive plasma concentrations above the LLOQ and at least one following C_{max} .

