4.3. Justification for Dose

Subjects will be treated with oral 100 mg C21 or placebo b.i.d. for 14 days.

The results of the completed phase 2 trial in COVID-19 subjects (VP-C21-006) and of the phase 1 trial in healthy subjects (VP-C21-003) indicate an acceptable safety and tolerability profile for the 100 mg b.i.d. dose. The risks of C21 in adults are considered primarily related to reversible alopecia seen at the higher dose of 200 mg b.i.d. In the phase 2 trial in COVID-19 subjects (VP-C21-006) and the phase 1 trial (VP-C21-003), the 100 mg b.i.d. dose did not cause any hair loss (Further details can be found in the IB). Alopecia is therefore not considered to present any significant safety risk to subjects in this trial.

In the phase 1 trial (VP-C21-003), 100 mg b.i.d. dosing prolonged the duration of the plasma concentration at therapeutic relevant levels. After oral administration, C21 was rapidly absorbed. On Day 8, median t_{max} was 0.33 hours after each dose post-dose, and C21 was measurable in plasma until 4-6 hours after the first and second dose. Lower doses than 100 mg b.i.d. may not provide maximal efficacy benefit.

In the completed phase 2 trial (VP-C21-006) in COVID-19 subjects, treatment with 100 mg b.i.d. for 7 days, reduced the need for extended oxygen supplementation.

The recently completed phase 2 trial (VP-C21-006) indicates that C21 can prevent hypoxic critical illness and based on the course of the disease, there is a strong rational to extend the treatment duration from 7 to 14 days. Furthermore, 27% of subjects within the C21 arm were still in need of oxygen (vs 45% on placebo) at the end of the 7 days treatment, highlighting an opportunity to treat for a longer period to gain additional benefit, with the aim of returning patients to normoxia.

There is not enough evidence to treat beyond 14 days at this stage.

Based on the above, C21 will be administered at an oral dose of 100 mg b.i.d. for 14 days in the present trial.

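### SAP 12.7.2 treats a BQL sample at 6 h as missing with no exception for C6, so the C6 summary runs high whenever any subject is BQL at 6 h and can disagree with the 12.7.1 concentration table

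*SAP*

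**What the plan says.** Protocol 8.6 and SAP 12.7.2 both list C6 among the PK variables. The SAP defines it as "Actual plasma concentration of C21 at 6 hours after IMP administration" and assigns its analysis to SAS, while the other parameters come from WinNonlin.

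For values below the quantifiable limit, SAP 12.7.2 gives two rules. Early in the profile: "In estimating the PK parameters, BQL values at the beginning of the profile will be set to zero". Later in the profile: "BQL values that occur after the first quantifiable point will be considered missing". Neither is restricted to particular parameters. Descriptive statistics, including n, mean and geometric mean, "will be used to summarize the calculated PK parameters by treatment"; only t_max has a different set of statistics.

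SAP 12.7.1 covers the concentration table, which includes the 6 h time point. There, concentrations "below the quantifiable limit (BQL) will be set to" half "the lower limit of quantification (LLOQ) in the computation of mean concentration values". It adds a display rule: "If 50% of the subjects at a given time point have values BQL then the descriptive statistics will not be presented", and the mean and minimum are then shown as BQL.

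On how long the drug can be measured, Protocol 4.3 reports that on Day 8 of a phase 1 trial C21 was "measurable in plasma until 4-6 hours after the first and second dose". The last PK sample in this trial is at 6 h (Protocol 8.6).

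**The concern.** Treating late BQL values as missing is a reasonable convention when a terminal slope or an area is being fitted. C6 is different: it is itself one concentration. If a BQL result at 6 h is missing, that subject has no C6, and the summary is taken over subjects who were still quantifiable at that time. The omission depends on the value being measured, so it cannot be neutral.

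The sample falls at the edge of the measurable window that the protocol reports, so BQL results there are plausible. What is at stake is a correct description of how much drug remains 6 hours after a dose, and agreement between the parameter table and the concentration table, which draw on the same blood sample.

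**Working it through.** The documents give no figure for C6, so there is nothing to reproduce. The check follows the rules through and then sizes the effect under stated assumptions.

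**1. Which rule reaches the 6 h sample.** The PK analysis set (SAP 9.5.5) requires at least one quantifiable sample after dosing, and 6 h is the last sampling time. For a subject in this set, a BQL value at 6 h therefore comes after a quantifiable one. The missing rule applies, not the zero rule.

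**2. Direction.** Let k subjects be retained with mean M_R and m subjects omitted with mean M_O. The all-subject mean is (k·M_R + m·M_O)/(k + m), so

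M_R − M_all = [m/(k + m)] × (M_R − M_O).

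Every omitted value is below the LLOQ and every retained value is at or above it, so this is positive whenever both k and m are at least 1. The same holds on the log scale for the geometric mean. No distribution is assumed.

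**3. Five-subject illustration (values invented).** Five on C21 is an assumption: 1:1 allocation among about 10 PK subjects, placebo included (SAP 9.5.5). Take LLOQ = 1 and 6 h values 3, 2, 1.5, BQL, BQL.

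- C6 mean under 12.7.2: (3 + 2 + 1.5)/3 = 2.17, n = 3.
- 6 h mean under 12.7.1: (3 + 2 + 1.5 + 0.5 + 0.5)/5 = 1.50, n = 5. Two of five is 40% BQL, so the display rule is not triggered.
- Lowest possible true mean, both BQL values 0: 6.5/5 = 1.30.
- Highest possible true mean, both BQL values at the LLOQ: 8.5/5 = 1.70.

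The 12.7.2 figure lies above any value the five-subject mean could take.

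**4. Size under a log-normal model.** The LLOQ, the BQL share p and the between-subject spread are not given, so all three are assumed. With log-scale SD σ, and z the p-quantile of the standard normal:

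- Geometric mean, BQL missing ÷ true: exp[σ·φ(z)/(1 − p)]
- Arithmetic mean, BQL missing ÷ true: Φ(σ − z)/(1 − p)

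Here σ = √ln(1 + CV²), which is 0.472 for CV 50% and 0.833 for CV 100%. A wider case, geometric SD 2.5, has σ = ln 2.5 = 0.916. The factor φ(z)/(1 − p) is 0.195, 0.350, 0.644 and 0.966 for p = 10, 20, 40 and 60%.

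| BQL share at 6 h | Geometric mean, CV 50% | Geometric mean, CV 100% | Geometric mean, geometric SD 2.5 | Arithmetic mean, CV 50% | Arithmetic mean, CV 100% |
|---|---|---|---|---|---|
| 10% | 1.10 | 1.18 | 1.20 | 1.07 | 1.09 |
| 20% | 1.18 | 1.34 | 1.38 | 1.13 | 1.19 |
| 40% | 1.36 | 1.71 | 1.80 | 1.28 | 1.44 |
| 60% | 1.58 | 2.23 | 2.42 | 1.47 | 1.80 |

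Simulation with 2,000,000 draws gave the same ratios for the two CV cases. Half-LLOQ substitution is not exact either. At BQL shares of 10-40%, where 12.7.1 would still print a mean, it gave 0.92 to 0.99 of the true arithmetic mean and 0.87 to 0.97 of the true geometric mean.

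**5. How often it would occur.** With five subjects, the chance of at least one BQL at 6 h is 1 − (1 − p)^5: 67%, 92% and 99% for p = 20, 40 and 60%.

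**6. What the two tables would show.** The 12.7.1 trigger is read here as half or more. With one or two of five BQL, both tables print a mean and the two differ. With three or four BQL, the concentration table shows BQL while the C6 table prints a mean from two subjects or one. The chance of three or more BQL is 6%, 32% and 68% for the same three shares.

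**The case against.** The strongest argument is about intent. The SAP takes C6 out of the WinNonlin work and calls it an actual concentration, so the authors may have meant the BQL rules in 12.7.2 for non-compartmental fitting only. That is possible. The text, however, applies those rules to the PK parameters without limit, and C6 is listed as one. If the narrower scope was meant, a sentence should say so.

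It can also be said that little is lost, because the 6 h sample appears in the 12.7.1 table, the C6 summary reports its own n, and collected data are listed. This stands in part. A reader might infer that the plan conceals how many subjects had no measurable drug at 6 h. It does not: a reduced n would show it, though less directly than a BQL count.

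Other tempting readings go beyond the documents:

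- **That C21 has gone by 4-6 h.** The protocol says it was measurable until then, on Day 8 of a phase 1 trial that it describes as in healthy subjects. That range reaches the 6 h sample. Here sampling follows the first dose in COVID-19 patients, so how often BQL occurs is unknown.
- **That the summary keeps only slow eliminators.** It keeps subjects with higher 6 h concentrations, whatever the reason. Low absorption is another possible cause of a BQL value; the protocol's risk table notes substantially lower exposure when fed.
- **That the report will always carry two different 6 h averages.** It will not if nobody is BQL, and once half are BQL the 12.7.1 table shows no mean.
- **That C6 is a finding on which the trial turns.** Neither document says so.

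**Conclusion.** The point holds as a defect in a stated rule. As written, SAP 12.7.2 drops any subject BQL at 6 h from the C6 summary, and the upward direction is certain whenever at least one such subject exists. Its size rests on assumptions: the geometric mean is inflated about 1.1 to 2.2 times for BQL shares of 10-60% and CVs of 50-100%, up to about 2.4 times at a geometric SD of 2.5, and not at all if no subject is BQL. The inconsistency with 12.7.1 is on the face of the text and needs no assumption.

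The importance is low. C6 is descriptive, about five C21 subjects are expected, and SAP 12.7 allows the PK data to be listed only. No efficacy conclusion depends on it.

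**What to change.** In SAP 12.7.2, state that setting late BQL values to missing applies to lambda-z and AUC estimation only. State that C6 is summarised with the 12.7.1 handling: half the LLOQ, together with the 50% display rule. Report the number and percentage of subjects BQL at 6 h beside the C6 summary.

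This costs one or two sentences in the SAP and one extra line in a table. It needs no new data, and PK analysis is done after unblinding, so trial conduct is not affected.
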